Regional Health Command-Central (RHC-C)
Institutional Review Board
Brooke Army Medical Center

**HUMAN SUBJECTS RESEARCH
PROTOCOL APPLICATION – Part B**

1
2
3
4
5
6
7
8
9
10
11 **1. PROTOCOL TITLE:** Nasally Inhaled Isopropyl Alcohol Versus Oral Ondansetron for the Treatment of Nausea in the
12 Emergency Department: A Double-Blind Randomized Controlled Trial

13
14 **2. ABSTRACT.** Nasally inhaled Isopropyl alcohol (ISO) has outperformed placebo in treating nausea among Emergency
15 Department (ED) patients.¹ Inhalation of ISO pads is without known adverse effects,²⁻⁴ relatively inexpensive and readily
16 available compared with antiemetic drugs, making ISO a potentially safer, cost effective and faster antiemetic intervention.
17 This agent has yet to be compared to conventional, commonly-used anti-emetics in randomized controlled trials. This study
18 will study the efficacy of ISO and conventional anti-emetics with three study arms: (1) inhaled isopropyl alcohol plus oral
19 ondansetron; (2) inhaled isopropyl alcohol plus oral placebo; (3) inhaled placebo plus oral ondansetron.

20
21 **3. OBJECTIVES/SPECIFIC AIMS/RESEARCH QUESTIONS.** The purpose of the study is to determine whether nasally
22 inhaled isopropyl alcohol provides better nausea relief compared to ondansetron oral solution in patients presenting to the
23 ED with nausea.

24
25 **4. MILITARY RELEVANCE.** Nausea is a common complaint seen not only in the ED but also in multiple deployed
26 medical settings. Establishing the use of inhaled ISO for nausea and/or vomiting as an evidence-based intervention
27 outperforming antiemetic drugs may relieve the nausea and/or vomiting symptoms to a significant degree and in a shorter
28 amount of time. ISO preps are readily available in every military/deployed medical setting. If nausea in ED patients can
29 be controlled with inhaled ISO, then its use can possibly be extended in other settings, specifically pre-hospital or combat
30 use. Inhaled ISO is less expensive and has been proven safer than antiemetic drugs.⁴

31
32 **5. BACKGROUND AND SIGNIFICANCE.** A recent Cochrane review of aromatherapy for the treatment of nausea
33 investigated 1386 articles; 44 articles were deemed relevant.⁴ Nine of these specifically studied ISO inhalation in post-
34 operative patients. Summation of this literature is challenging given heterogeneous outcome measures. Several non-
35 blinded studies examined time to 50% reduction in nausea as measured on a verbal numerical rating scale (VNRS), 0-11,
36 finding isopropyl alcohol achieved this more rapidly than conventional anti-emetics such as promethazine and
37 ondansetron (times ranging 6.5-15.0 minutes).⁵⁻⁷ A fourth study was single-blinded and reported absolute VNRS (0-11)
38 for isopropyl alcohol versus usual anti-emetics (not otherwise specified). This study found scores decreased from a mean
39 of 5.7 pre-inhalation to 2.7 post-inhalation though this was not significantly better than the usual care arm.⁸ A fifth study
40 compared inhaled isopropyl alcohol plus ondansetron versus ondansetron alone concluding no significant differences in
41 nausea as measured on a 0-11 VNRS.⁹ An additional three studies compared inhaled isopropyl alcohol to inhaled
42 placebo, all of which concluding that isopropyl alcohol resulted in superior nausea relief.¹⁰⁻¹² Finally, a randomized trial
43 with three arms including inhaled peppermint, inhaled isopropyl alcohol, and inhaled placebo found no difference in
44 nausea scores as measured by a visual analogue scale (VAS).¹³ In total, the Cochrane review article broadly concluded
45 efficacy for isopropyl alcohol in treating post-operative nausea and vomiting. These studies were limited in that none were
46 performed in an outpatient or pre-hospital setting. More recently, a randomized controlled trial at San Antonio Military
47 Medical Center (SAMMC) demonstrated efficacy at 10 minutes among ED patients with nausea or vomiting.¹ Of note,
48 although traditional anti-emetics (e.g., ondansetron, promethazine, metoclopramide) have demonstrated efficacy in
49 specific patient populations such as cancer patients receiving chemotherapy,¹⁴ multiple studies have found these agents
50 are no better than placebo in treating nausea among undifferentiated ED patients.¹⁵⁻¹⁷ Despite the absence of efficacy
51 data, these agents are frequently used in the treatment of nausea among ED patients. Our objective is to compare the
52 efficacy of inhaled isopropyl alcohol to ondansetron in treating nausea among undifferentiated patients.

53
54 **6. RESEARCH DESIGN** This study is a prospective randomized controlled trial. We will test the hypothesis that nasally-
55 inhaled ISO plus oral placebo has greater anti-emetic efficacy compared to nasally-inhaled saline plus oral ondansetron
56 oral solution. By design, the study will be double-blinded insofar as neither investigators nor subjects will be notified of the
57 identity of the substances they are inhaling or swallowing. We anticipate blinding to scent may be challenging and the

58 study will include a post-study survey to ascertain the extent to which this blinding was achieved. Potential subjects are
59 those presenting to the SAMMC ED with symptoms of nausea and/or vomiting. For the purposes of this study, nausea is
60 defined as the subjective sensation associated with the urge to vomit, and vomiting is defined as the forceful expulsion of
61 gastric contents. Investigators will approach subjects at the time of initial triage and/or while in the waiting room. This will
62 mitigate interruptions in the subject's treatment, possible withdrawals from the control group, and lack of subject interest in
63 the study. Part of the screening process will entail solicitation of nausea on a VNRS scored from 0-10 with those patients
64 reporting scores of 3 or greater eligible for study. Informed consent will be obtained from each subject. Upon enrollment,
65 a study team member will record the patient's date of visit, FMP + sponsor social security number, and date of birth
66 (month, day, year) on the study key which will be maintained in a locked cabinet in the principal investigator's office.
67

68 Regarding blinding, subjects will be informed they will be nasally inhaling one of two common medical preparation pads
69 saturated with different ingredients and taking orally one of two common oral solution substances. Subjects will be
70 allocated to one of three arms: (1) inhaled isopropyl alcohol plus oral ondansetron; (2) inhaled isopropyl alcohol plus oral
71 placebo; (3) inhaled placebo plus oral ondansetron. No subject will receive both inhaled and oral placebo; all subjects will
72 be allocated to at least one therapeutic intervention for nausea. Both investigators and study subjects will be blinded to
73 subject allocation. Randomization will be performed prior to study start with a computer-generated assignment (simple
74 randomization sequence) by an individual not otherwise involved in the study. A copy of the randomization key will be in a
75 sealed envelope and placed in the study file box along with study packets as to be readily available in the ED in case un-

97 be encouraged to take inhalations as frequently and deeply as they feel is necessary to achieve nausea relief. If a subject
98 is unable to or prefers assistance with nasal inhalation or oral solution consumption, the patient's nurse will provide any
99 assistance needed. The investigator will remain at arm's length from the patient at all times to avoid detecting prep pad
100 scent. Additionally, investigators will also instruct subjects to avoid any behavior or actions during the study that would
101 indicate which preparation pad is being used. Examples of behavior to avoid would be verbally describing the scent of the
102 preparation pad or taste of the oral solution.
103

104 The investigators will record their findings on data collection forms. The primary outcome will be nausea as measured on
105 a 10 cm visual analogue scale (VAS) at 30 minutes. This time horizon was selected as ondansetron's labeled use is
106 administration 30 minutes prior to receipt of chemotherapy to treat chemotherapy-related nausea. Nausea measurements
107 will also be collected at 10, 20, 40, 50, and 60 minutes, and then every hour up to 5 hours, then at disposition at which
108 time the patient will provide one final nausea VAS score. The study team member will not be present in the patient's room
109 during the intervals between these evaluations. At the time of each nausea measurement, patients will be offered another
110 preparation pad (up to ten pads). We will notify the patient's treating provider to prompt consideration for treatment with a
111 rescue anti-emetic (such as metoclopramide or promethazine) if the patient vomits or if the patient requests an anti-emetic
112 at any time. At the time of each nausea measurement, a pain score will also be measured on a 10 cm VAS. At the time
113 of final disposition, the patient will provide a satisfaction score on a 10-cm VAS and be asked to indicate his/her belief as
114 to whether the pad was a treatment or placebo and whether the oral solution was a treatment or placebo. Similarly, at

study conclusion the patient's provider will be asked to indicate his/her belief as to whether the pad was a treatment or placebo and whether the oral solution was a treatment or placebo. Other data collected will include times and doses for all medications (including preparation pads) and fluids administered, episodes of vomiting (defined as forceful expulsion of gastric contents separated by at least 2 minutes), disposition (admission versus discharge), final clinical impression at the time of disposition, and time to disposition. Subjects will be followed and data collected for the entirety of their ED stay. A lockbox identified as "Nausea study" will be maintained in the ED for data collection form storage to which only the investigators and ED staff will have the key. ISO prep pads, saline prep pads, Ondansetron oral solution, and its matching placebo do not require storage in a hazardous material cabinet. This study will be registered on ClinicalTrials.gov.

Subjects will comprise a convenience sample. Study investigators will log hours of recruitment on a password-protected excel spreadsheet which will not contain any PHI. To confirm the sample is representative of all patients presenting to the ED with nausea, we will examine CHCS ad hoc data already generated by the ED on a routine basis for performance improvement purposes for all patients whose registration chief complaint contains either the words "nausea" or "vomiting" including patients not enrolled in our study. Comparison of the characteristics of enrolled patients with patients not enrolled will enable us to establish whether there was selection bias in our study. These patients' FMP prefix and sponsor last 4 will be cross-referenced against our enrolled subjects. With our enrolled subjects removed, we will extract only the following data: age, sex, ESI category, diagnoses, receipt of any anti-emetics to include drugs and doses, and whether or not admitted. Any patient on the Ad Hoc list who is 89 or older will be recorded as ≥89. We will also need to access cross-reference the SSN or MRN of all these patients along with the dates of treatment data to establish whether a given CHCS data point represents a visit from a patients recruited into the study or a non-recruited patient. No PHI will be extracted from the ad hoc data. These extracted data will be maintained on a password-protected, CAC-enabled government laptop.

The prospective chart review (CHCS ad hoc data query) portion of the study will be conducted under a waiver of informed consent. This portion of the research involved no more than minimal risk to subjects as medical records are reviewed for limited information that is not of a sensitive nature. Adequate precautions are in place to protect the confidentiality of the information. Waiving consent will not adversely affect the rights and welfare of the subjects as the study reviews medical records for care already provided and cannot impact or change the care received. The research could not be practically carried out without the waiver as contacting hundreds of subjects is not feasible for review of medical records for information that would not change the care that the subjects have already received. A HIPAA Waiver of Authorization is also submitted to access patients' medical records for the prospective chart review portion of the study.

This study will pose no more than minimal risk to participants. Our use of isopropyl alcohol and ondansetron will not significantly increase the risks associated with the use of these medications in our study. These medications should quality for IND exemption (see section 7.2.1). All data for research purposes will be collected by non-invasive means.

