7. RESEARCH PLAN

7.1 Selection of Subjects

7.1.1. Subject Population.

Patients ages 18 and older presenting to the Emergency department with a complaint of nausea and/or vomiting. All presumed causes of nausea will be included. Inclusion/exclusion criterion is based on safety considerations that were discussed with SAMMC clinical pharmacist. Other considerations are circumstances that altered smell or perception, exogenous emetics, concomitant antiemetic therapy and alcohol exposure. No specimens will be obtained.

7.1.2. Source of Research Material.

Source of Research Material	Conducted for Clinical Purposes(Y/N)	Conducted for Research Purposes
VAS Nausea Score	N	Y
Case Report Form	N	Y

VAS Patient Satisfaction Survey	N	Y
CHCS ad hoc data for all ED patients with nausea or vomiting including those not enrolled in the study for purpose of ruling out selection bias in study population	N	Y

34
 35 **7.1.3. Inclusion and Exclusion Criteria.**

36 Inclusion Criteria:

- 37 (a) ages 18 and older
- 38 (b) complaint of nausea and/or vomiting reported at 3 or above on VRNS at the time of ED triage

39
 70 Exclusion Criteria:

- 71 (a) allergy to isopropyl alcohol or ondansetron
- 72 (b) inability to breathe through nose (e.g., recent upper respiratory infection)
- 73 (c) intake of cefoperazone, disulfiram, or metronidazole within the last 24 hours
- 74 (d) mental status precluding informed consent including intoxication
- 75 (e) known QT-prolongation
- 76 (f) clinical suspicion for serotonin syndrome
- 77 (g) intravenous catheter in place prior to study start
- 78 (h) medications administered since patient arrival to ED (e.g., in triage)
- 79 (i) suspected or known pregnancy

30
 31 **7.1.4. Description of the Recruitment and Prescreening Process.** ED providers and RN triage nursing staff (none of
 32 whom will be study team members) will be apprised of the study inclusion criteria to notify study team members of potential
 33 subjects. Potential subjects will be asked to quantify their nausea on a VNRS (0-10) for the purposes of discerning study
 34 eligibility by triage nurses, the RNs assigned to the patient, or the patient's provider. Efforts will be made to perform this
 35 prescreening process early in the patient's ED course (ideally at the time of triage or initial arrival to treatment room). No
 36 other history, physical exam or other evaluations beyond those normally conducted as the standard of care shall be performed

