 39 sex, and nausea VNRS will be recorded for all patients declining to participate in the study. No personal health information
 40 will be collected on these patients.

13 **7.1.7. Compensation for participation.** No compensation will be provided to the subjects.

14
15 **7.2 Drugs, Dietary Supplements, Biologics, or Devices.**

16
17 **7.2.1 Drugs**

18 Professional Disposable International (PDI) Alcohol prep pads. NDC 10819-3914-2, C69900

19 Professional Disposable International (PDI) Sterile Saline prep pads. C22370

20 Ondansetron Oral Solution 4mg/5ml . NDC 0054-0064-47. 5 ml (4 mg) per subject study dose.

21 Placebo oral solution – 0.25ml of Oral Sweet Sugar Free NDC 0574-0302-16 with 4.75ml of Sterile Water for Irrigation

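### The selection-bias check in Section 6 cannot establish selection bias as written: eligibility is mixed with selection, anti-emetic receipt is largely set by allocation, and ESI has only one side

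*Combined protocol and SAP*

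**What the plan says.** Section 6 recruits a convenience sample and states two aims for a query of routine ED records. The first is "To confirm the sample is representative of all patients presenting to the ED with nausea". The second is the inference that "Comparison of the characteristics of enrolled patients with patients not enrolled will enable us to establish whether there was selection bias in our study". The table in Section 7.1.2 gives the purpose as ruling out selection bias.

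The query is run "for all patients whose registration chief complaint contains either the words" nausea or vomiting. Enrolled subjects are then removed, and only these fields are extracted for the remainder: "age, sex, ESI category, diagnoses, receipt of any anti-emetics to include drugs and doses, and whether or not admitted". Recruitment hours are logged, but no use of the log is stated.

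Eligibility is much narrower than the list. Section 7.1.3 requires "a) ages 18 and older" and a nausea rating of at least 3. Among its exclusions are an intravenous catheter already in place, any medication since arrival, and known or suspected pregnancy. Section 7.1.6 adds a separate log of refusals: data on age, "sex, and nausea VNRS will be recorded for all patients declining to participate in the study". No analysis of that log is described, and Section 7.4.3 gives no method for any representativeness comparison.

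**The concern.** A contrast between enrolled and non-enrolled patients shows selection bias only if both groups could have been enrolled. Here the non-enrolled group may contain minors, patients with mild nausea, and patients already cannulated or medicated. Differences produced by the entry criteria would read as selection, and genuine selection among eligible patients could be offset and missed.

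Two of the six fields have a further problem. Anti-emetic receipt in enrolled patients is mostly a consequence of the trial. ESI has no stated source for enrolled patients: it is taken after they have been removed from the list, and the data list in Section 7.3.2 does not include it.

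At stake is the chart comparison that the protocol offers in support of its convenience sample, and therefore what can be said about the patients to whom the result applies.

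**Working it through.** The plan gives no sample size, test or threshold for this check, so there is no figure to reproduce. The only plan number used below is the enrolment target in Section 7.4.1: 120 + 60 = 180. All other rates are assumptions, because the documents give no age mix, admission rate or comparator size.

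**1. Can the entry criteria be applied to the extract afterwards?** Age can be filtered. Diagnoses might identify some exclusions, such as pregnancy. The nausea rating, a prior catheter and prior medication are not among the six fields. Visit time is not extracted either, so the logged recruitment hours cannot be matched to the extract.

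**2. Age, with perfectly representative adult enrolment.** Assume adults have mean age 42 (SD 17), minors have mean 8 (SD 5), and a share q of listed visits are minors.
- Gap in means = q × (42 − 8) = 34q.
- Comparator variance = (1 − q) × 17² + q × 5² + q(1 − q) × 34².
- z = gap / √(17²/180 + variance/m), where m is the number of comparator visits.

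| q | Gap (years) | Variance | z, m = 1,000 | z, m = 300 |
|---|---|---|---|---|
| 10% | 3.4 | 366.6 | 2.4 | 2.0 |
| 20% | 6.8 | 421.2 | 4.8 | 3.9 |
| 30% | 10.2 | 452.6 | 7.1 | 5.8 |

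With an adult filter q = 0, and this gap disappears.

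**3. Admission, with non-selective enrolment among eligible patients.** Let a share q of the comparator be ineligible. Comparator rate = (1 − q) × eligible rate + q × ineligible rate.
- Rates of 20% (eligible) and 40% (ineligible): q = 0.2, 0.4 and 0.6 give 24%, 28% and 32% against 20% enrolled, an artefact of 4, 8 or 12 points. With 180 enrolled and 1,000 comparators, a two-sided 5% test would be significant about 20%, 62% and 92% of the time.
- Rates of 20% and 25%: the artefact is only 1, 2 or 3 points, significant about 5%, 8% and 13% of the time.

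The size therefore depends heavily on how different the ineligible patients are.

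**4. Masking.** Suppose 25% of enrolled patients are admitted, against 15% of eligible non-enrolled patients and 40% of ineligible patients, who make up 40% of the comparator. The comparator rate is 0.6 × 15% + 0.4 × 40% = 9% + 16% = 25%. A real 10-point selection effect shows as no difference.

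**5. Anti-emetic receipt.** Two of the three arms receive ondansetron. With equal allocation (assumed), the enrolled rate is 2/3 + r/3, where r is the share of the oral-placebo arm given rescue: 67%, 75% and 83% for r = 0, 0.25 and 0.5. At least two thirds is set by design, whoever is enrolled. The other side is affected too. Section 7.2.1 says ondansetron is part of the department's triage protocols, so patients treated that way are excluded from the trial but stay in the comparator.

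**The case against.** The strongest reply is that the check has two aims. For describing how the sample compares with all ED nausea patients, the unfiltered list is the right one, and a difference caused by eligibility is real non-representativeness. That stands. A reader might infer that the whole check is uninformative, but the documents do not support this. Age and sex are unaffected by allocation and stay informative, age can be filtered, and only one of the six fields is driven by allocation, in part. The oral-placebo arm and rescue use are not fixed by design. Times and doses of all medications are recorded for enrolled patients, so study drug can be separated from the rest.

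The ESI gap may be one of wording, since enrolled visits start on the same source list. It still needs stating, because the plan extracts the field only after they are removed.

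A reader might also take the refusal log as the best comparator. It is not. Under Section 7.1.6 the investigator asks about willingness first and verifies exclusions only if the patient agrees, so some decliners may be ineligible. The log also covers only approached patients and says nothing about those who came outside recruitment hours.

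Finally, the z-values and significance rates presuppose a test that the protocol does not specify, and they rest on assumed rates. They show that the artefact can be large, not that it will be.

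**Conclusion.** The concern holds for the selection-bias claim. As written, the comparison mixes eligibility with convenience selection, includes a variable largely determined by allocation, and has ESI for one side only. It can describe differences between the sample and other ED nausea visits. It cannot establish or rule out selection bias.

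Two parts rest on the text alone: the unrestricted list and the one-sided ESI field. The two-thirds figure for anti-emetics needs equal allocation. The size of any artefact is unknown: 3.4 to 10.2 years in age and 1 to 12 points in admission across the scenarios shown, all on assumed inputs.

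It would be wrong to infer any effect on the treatment comparison. Randomisation, the primary analysis and the sample size are untouched. This is a minor point about generalisability, worth correcting because correction is cheap.

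**What to change.** In Section 6, keep the unfiltered list for the aim of describing the sample against all ED nausea patients. For the selection-bias comparison:

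- Restrict the list to visits aged 18 and older.
- Extract ESI for enrolled subjects from the same list before removing them.
- Compare only anti-emetics other than study drug, or report anti-emetic receipt descriptively.
- Add visit date and time to the extraction, so that results can be shown inside and outside the logged recruitment hours. This must be settled before extraction.
- Add a supplementary comparison with approached patients who declined, on age, sex and VNRS, noting that their exclusions may not have been verified.
- Report standardised differences, and name the method in Section 7.4.3.
- In Sections 6 and 7.1.2, replace *establish* and *ruling out* with *describe*. Even after the adult filter, patients with a rating below 3, a prior catheter or prior medication cannot be removed using the listed fields.

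The cost is a filter, an added visit date-and-time field with a small change to the waiver request, one extra table, and fewer comparator visits.
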